5.3.3 Cross-Over Prevention Procedures

Epic coding will ensure control arm providers cannot access intervention components. Periodic checks will be conducted to ensure this remains in place as planned.

If a control arm provider reaches out for a consultation, the CAP may still discuss treatment options and make recommendations as they would as part of their normal role.

The behavioral health navigator will be responsible for ensuring that the services s/he offers and the bridging therapy are only accessible to intervention arm patients and providers.

Patients who change to the panel of a provider assigned to a different arm during the 6 month follow-up period will remain in the arm of their original prescriber for the 6 month follow up period.

5.4 Withdrawals

The algorithm and workflow will be applied to every randomized clinician and eligible patient enrolled at each health system.

Waivers of consent will be obtained from the local Institutional Review Board (IRB) at each site. Neither providers nor patient-subjects may withdraw given the pragmatic design and intent-to-treat analysis

plan. Subjects remain in the study regardless of their acceptability or degree of exposure to interventional components, given the encouragement trial design.

5.5 Opting Out of Study Components

Medication alert: Providers may cancel the medication alert by both de-selecting the antipsychotic in Epic and not ordering any extra support (i.e., CAP consultation, BH navigation, expedited psychotherapy access).

CAP review: Intervention arm prescribers may not opt out of passive CAP reviews. Control arm prescribers are not included in CAP review.

- The CAP is automatically informed of the need for a passive review (i.e., provider did not order a consult) after eligibility is confirmed.
- The CAP is automatically informed of the need for an active review (i.e., provider ordered a consult), prior to eligibility confirmation to avoid any delay.
 - If the patient is deemed ineligible upon review, other study services will not be offered to the patient/family.
- Passive CAP review will still occur if the clinician clicked an exclusion in the BPA (e.g., autism) and the patient is subsequently verified to be eligible. That is, study staff (not the prescriber) determines study eligibility. The prescriber maintains his/her clinical autonomy and may opt not to follow the CAP's treatment recommendations. No treatments or medications are withheld at any time.

CAP consultation: The study CAP may still reach out to an intervention arm prescriber to discuss a case when a CAP consult was not ordered. The prescriber may decide not to respond to or schedule with the CAP. The prescriber maintains his/her clinical autonomy and may opt not to follow the CAP's treatment recommendations. No treatments or medications are withheld at any time. Secondary outcomes include: the percentage of clinicians that follow CAP advice; the percentage of patients with a change to psychotropic medication treatment plan following CAP review; and model stage of departure from the algorithm (first line, second line, third line treatments prior to antipsychotic).

Behavioral health navigation: Intervention arm providers may decline behavioral health navigation for their patient by responding to a staff message from the navigator. Families/teens contacted by the navigator may decline behavioral health navigation at any time. Secondary outcomes include the percentage of patients that agree to behavioral health navigation, and the percent of patient that attend 2 or more face-to-face therapy sessions.

Expedited access to bridging therapy: Intervention arm providers may decline bridging therapy for the patient/family by responding to a staff message from the navigator. Families/teens offered study bridging therapy may decline it at any time. The percent of patients that attend two or more bridging sessions with a study therapist is a secondary outcome of the study.

6 CONTROL ARM

The control arm advance communication and medication alert inform the prescriber of *Choosing Wisely*® recommendations regarding antipsychotic medications in children and adolescents. These guidelines were developed by the American Psychiatric Association (APA). Available at: <http://www.choosingwisely.org/clinician-lists/american-psychiatric-association-antipsychotics-in-children-or-adolescents/>

The firing of the control arm medication alert will add the patient to the study enrollment log as a comparison case. Study staff will confirm eligibility via blinded chart review for all patients logged.

The follow up period is 6 months.

Should a control arm provider find SUAY orders in Epic and attempt to order a study service (e.g., navigation, expedited access to bridging therapy), an alert will fire to inform him/her that the patient is not eligible for the service.

7 INTERVENTION ARM

7.1 Intervention Arm Medication Alert Intervention Description

Randomized providers at each site will be informed in advance of the quality improvement study being conducted. The communication will inform intervention arm providers of the nature of the interventional components (e.g., medication alert, case review by a child and adolescent psychiatrist, behavioral health navigation, bridging therapy).

The medication alert is triggered by entering an antipsychotic in Epic for a target patient. See Appendix B. The patient is added to a study enrollment log at the time of the encounter. The intervention arm medication alert links providers to a document containing *Choosing Wisely*[®] guidelines, the national expert consensus panel clinical guidelines developed for SUAY, and contextual study information.

Within the alert, the prescriber has the option to:

- keep/remove the medication entered (default = remove)
- keep/remove an order for a provider-to-provider consult with the CAP (default = keep)
- keep/remove an order for BH navigation for the patient (default = keep)
- keep/remove an order for expedited access to bridging therapy for the patient (default = keep)

The study CAP is automatically notified that a review is needed each time an intervention arm provider actively orders a CAP review in the alert and after a patient is verified eligible when a consult is not actively ordered.

7.2 Eligibility Confirmation

Study staff (PI or delegate) blinded to arm assignment will conduct a focused medical record review within 3 business days of the case being logged to the study when the alert fired. The staff person will utilize a checklist of study inclusion and exclusion criteria for this review.

Patients found not to meet criteria will be flagged as ineligible and the reason(s) noted in the study log. Patients found to meet all study criteria will be flagged as eligible. Upon being thus flagged, eligible intervention subjects will be ‘released’ to the CAP and navigator.

7.3 CAP Case Review and Consultation Intervention Description

Expert clinical guidance for safer prescribing of antipsychotics to youth was developed in Phase 1 of the contract. See Appendix C. This will guide the CAP as s/he reviews the clinical scenario around each antipsychotic order (e.g., treatment history, current treatments, diagnoses) to determine the next best step in the treatment plan. If information is missing or the prescription is not in line with expert clinical guidance, the CAP may attempt to contact the prescriber to discuss the appropriateness of proceeding to an antipsychotic for the case and possible revisions to the treatment plan. The CAP will provide the prescriber with a written recommendations summary for every review completed. A standardized template will be used. The CAP’s recommendations may be noted in the medical record.

The prescriber is free to accept or disregard the CAP's recommendations. There are no negative consequences to providers if CAP treatment recommendations are not implemented. That is, the prescriber's clinical autonomy is in no way constrained or diminished.

7.3.1 Administration of CAP Case Review and Consultation

Case review of intervention arm patients will be conducted by a study CAP within 3 business days of receiving notification of the case at each site. If a provider-to-provider discussion is deemed necessary by the CAP and the prescriber did not order a consult directly, a virtual consult between the CAP and prescriber will be arranged within 2 weeks of the visit.

The CAP's review outcomes will be sent to the prescriber and may be noted in the patient's chart. The exact procedure will vary by site. The CAPs may also provide guidance to the navigator (e.g., patient is not a good candidate for telemental health, etc.)

Filing of the script is not delayed by the study while the review occurs. However, existing Washington State law requires antipsychotic scripts for children on Medicaid to be held at the pharmacy until pre-authorization is granted by the State. This process is outside the control of the project at KPWA.

CAP recommendations: A structured template will be used by all study CAPs to convey review outcomes and recommendations to prescribers. Feedback will be shared with the prescriber for every case reviewed. This includes situations where the CAP agrees with the antipsychotic order and/or if the CAP discussed the case with prescriber directly (e.g., by phone, email, or in person).

7.3.2 Procedures for Training Study CAPs and Fidelity Monitoring

[name] of Seattle Children's Hospital created and directs both the Second Opinion and Partnership Access Line programs based in Washington State. He will train study CAPs at other clinical sites, as needed, on the study protocol, SUAY guidelines, and CAP consultation best practices.

Site CAPs will meet by regular conference call to discuss fidelity to the SUAY clinical guidelines by anonymously discussing case examples. Recommendations will be periodically quality checked in Epic to ensure CAPs are adhering to and completing the structured recommendations template for the study.

7.4 Behavioral Health Navigation Description

Eligibility will be confirmed via medical record review within 3 business days of the patient being added to the study enrollment log at each site.

Initial provider outreach: The behavioral health navigator will contact intervention arm prescribers via staff message within 2 business days of the CAP providing his/her summary of review outcomes. When a provider actively ordered a study service for their patient, the navigator will send the provider a short message. When a study service was not explicitly ordered for an eligible patient, the navigator will introduce him/herself to the provider in a staff message, briefly describe the extra support the BH navigation can offer the patient, and inform the provider that s/he may respond by staff message to decline the extra support on behalf of the patient, if desired. If a provider contacts a navigator directly

to request a study service, the navigator will request that the provider order the requested service in Epic. Ordering the service in Epic will log the patient for study eligibility review. The navigator will contact the provider if the patient is subsequently deemed ineligible.

Existing guidelines all recommend that psychosocial interventions be tried before prescribing antipsychotic medications. Unless a provider actively declines the extra support, the navigator will contact the teen/family to offer behavioral health navigation.

Initial patient outreach: Waivers of consent/assent are obtained from the reviewing IRBs. BH navigators at each site will administer the equivalent of modified oral consent/assent by phone, as required by the local IRB, when calling to offer up to 6 months of navigation services. BH navigation is offered through the study at no additional cost.

Follow up patient outreach: If the teen/family agree to BH navigation, the navigator will initiate contact at least monthly during the 6 month follow up period to inquire about the child's status and re-evaluate barriers to access. The navigator will use motivational interviewing techniques (e.g., reflective listening, asking open ended questions) with the youth and/or parents to encourage them to engage in psychosocial treatments, attempt to motivate them to continue or restart therapy (as needed), and identify and help problem-solve ways to minimize barriers to starting or continuing therapy. When barriers exist, s/he will offer assistance in identifying behavioral health clinicians that may be a good fit for the family/teen, and further assess appropriateness of short-term bridging therapy.

The navigator will remind teens/families, as appropriate, that laboratory tests are due to be completed 3 months after starting an antipsychotic.

The navigator will note any medication side effect information incidentally reported by the teen/family in the phone note. If a reported side effect is burdensome, the navigator will encourage the patient or parent/guardian to contact their provider about their concern or side effect.

The navigator will follow the study *Safe Practice Protocol* if suicidal ideation is incidentally revealed by a subject during a BH navigation outreach call.

Ad hoc patient outreach: The navigator will reach out to assess barriers and attempt to motivate the teen/family to continue therapy if a BH appointment is missed and not rescheduled within 2 weeks.

Final patient outreach call: The navigator will conclude services with a review of the agreed upon plan for next steps and encouraging continued contact with the clinical care delivery system.

Follow up provider outreach: Following each outreach call, the navigator will secure message the prescriber with relevant updates, as needed.

7.4.1 Administration of BH Navigation Intervention

An Epic reporting workbench will be used to support BH navigation at each site. Navigators will be prompted to follow up with subjects at the appropriate time points, log outreach attempts and

outcomes, note subjects' acceptance or refusal of navigation and (if offered) short term bridging therapy, and track subject adherence to the treatment algorithm.

7.4.2 Procedures for Training of BH Navigators on Intervention

[name], LICSW of Kaiser Permanente Washington will serve as the lead behavioral health navigator and train SUAY behavioral health navigators at other clinical sites.

Navigators will meet regularly by phone to anonymously discuss any difficult cases and ensure fidelity to the protocol between the sites.

7.5 Short-Term Bridging Therapy Description

Either the study CAP or the prescribing clinician may decline bridging therapy for the subject based on the clinical scenario. The BH navigator will use a decision tree to further assess appropriateness of short-term bridging therapy. Any reason that bridging is not offered will be noted in the navigator's reporting workbench (e.g., declined by prescriber, CAP advised against, subject already engaged in therapy, etc.).

The BH navigator will administer modified oral consent/assent for bridging services, as required by the local IRB, schedule the initial session, and note if the teen/family requires a loaner device (e.g., tablet) if bridging visits are to be delivered via telemental health (TMH) video visits.

When TMH is to be delivered, a TMH privacy and safety plan with the subject prior to the first TMH session. The offer of TMH will be suspended if a privacy or safety concern is identified when the form is completed until a clinical decision can be made by the therapist. The plan identifies resources within and outside the home to ensure patient privacy during TMH sessions, and plan for any potential crises, safety concerns, or inability to contact the teen/family.

All bridging visits will be entered in Epic as patient visits. There will be no copays or other charges billed for these study-related visits.

7.5.1 Administration of Bridging Therapy

Each health system will identify 1 or more licensed and credentialed therapists to provide bridging therapy. Study sites will offer clinic-to-home telemental health (TMH) with a study therapist via HIPAA-compliant video visit technology when appropriate for and agreeable to the participant. Phone-based or in-person visits may be offered by sites if technical challenges or patient/family preference prohibit video-teleconferencing visits. If a televideo connection cannot be established, the therapist may reach out by phone to start (or complete) a TMH session without video.

Appointments and set up for TMH: Study staff will provide subjects with instructions for joining telemental health sessions, as appropriate. Appointment reminders will be sent. Appointment reminders for TMH sessions will include a link for the patient to join the next TMH session.

If a suitable personal device is not available for video-visits, study staff will provide an inexpensive, secure loaner device to the subject during their first appointment.

Content: The therapeutic content of bridging sessions is solely determined by the therapists delivering the care as informed by the consensus panel guidelines developed in Phase 1 and established, empirically supported treatments. The study is investigating methods to improve access and use of psychotherapy; not evaluating any specific psychotherapeutic interventions.

Duration and transition: Bridging will conclude after 9 sessions or when the patient can begin long-term, in-person therapy, whichever comes first. The extra support provided by the BH navigators includes helping the patient/family transition from bridging to ongoing psychosocial therapy when appropriate.

7.5.2 Procedures for Training of Therapists in Telemental Health

[name], MPH of Seattle Children’s Hospital will train study therapists in telemental health delivery best practices. She will meet by phone regularly with study therapists to discuss technical or other challenges to the telemental health. Protected health information (PHI) will not be shared.

8 STATISTICAL CONSIDERATIONS

8.1 Sample Size Considerations

We anticipate enrolling as many as 800 eligible patients in the trial (up to 400 per arm), with up to 360 eligible patients in each arm remaining enrolled at 6 months of follow-up (i.e., 10% lost to follow-up).

8.2 Primary Analysis Plan

Data will be collected from project tracking systems, the Epic EMR, and other health system data systems for analysis. Sites will securely transfer limited datasets to the data coordinating center at KPWHRI at defined intervals.

Data validation and quality assurance checks will be undertaken to ensure data collection during the study is sufficiently reliable.

We will use descriptive statistics to summarize adherence to the study algorithm. Specifically, we will summarize the patient characteristics (age, gender, race and ethnicity, diagnoses) of those individuals enrolled in the study and we will summarize clinician adherence to the algorithm protocol by provider specialty. Modal stage at deviation from the protocol will be evaluated among clinicians deviating from the protocol; additionally, modal algorithm stage of drop out among patients in the intervention arm who receive antipsychotic treatment during the 6 month window will be summarized. Our primary outcomes are percent of patients taking antipsychotic medication at 6 months post enrollment and total person-months of antipsychotic use by youth, based on medication order data. As secondary outcomes, we will also compare the percent of patients taking antipsychotic medication at 6 months post enrollment and total person-months of antipsychotic use by youth, based on prescription fill data.

We will also measure: the percentage of patients with a change to psychotropic medication treatment plan following second opinion review; percent of patients that agree to BH navigation; percent of patients that attend 2 or more bridging therapy sessions; and percent of patients that attend 2 or more face-to-face therapy sessions after transitioning from study bridging therapy to standard care.

In order to capture any negative unintended consequences, we will compare the number of emergency department visits, successful and unsuccessful suicide attempts, deaths, and hospital admissions between study arms over the 6 months following the intervention.

8.2.1 *Statistical Analysis Plan*

All primary analyses will follow an intent-to-treat approach, including all individuals assigned to an intervention arm regardless of the amount of intervention received. Non-inferiority evaluations will also be evaluated in a supplementary “as treated” analysis, comparing outcomes according to treatments actually received by patients during their observed period of follow-up. This supplemental comparison is useful in a non-inferiority assessment due to the fact that the alternative hypothesis of “no effect” is more likely in the presence of protocol violations and therefore the intent to treat approach will be anti-

conservative if many patients in the intervention arm, for example, revert to control. Also, non-inferiority of Emergency Department visit rate in the intervention arm compared to usual care control will only be assessed on final analysis if superiority is shown for the primary endpoint of no antipsychotic use at 6 months.

We will use Poisson regression to estimate (1) the percent of individuals using antipsychotics at 6 months post enrollment and (2) the total number of person-months of antipsychotic use by youth in the six month follow-up period, per provider medication orders, in each of the study arms. We will use generalized estimating equations(43) to estimate the parameters in the Poisson regression model. We will use the robust sandwich estimator to ensure correct standard errors for the intervention effect due to possible violation of the Poisson variance assumption(44); additionally, this will allow us to account for any clustering within clinics(43) and providers. Poisson regression allows comparison of relative incident rates among the intervention arms when outcomes are not rare(45). Additionally, Poisson regression will allow us to control for pre-specified baseline covariates (age, gender, and race) as well as site differences in any antipsychotic use and allow for straightforward estimation of site-specific intervention effects in sensitivity analyses. For a secondary analysis, we will repeat this approach defining antipsychotic use with prescription fill data rather than orders.

Data for our primary outcome of interest, any antipsychotic use, will be collected from electronic health records on provider orders. Electronic health record data on prescription fills will be used to assess the secondary outcome (antipsychotic medication fills). This means that traditional study drop-out due to premature participant withdrawal from the study will not lead to missing data in primary analyses. However, there will be the potential for differential follow-up rates among individuals due to youth disenrolling from their or their parent/guardian's health plan. Death is also a possibility, but unlikely. We will compare those youth for whom we are only able to collect outcome information for a portion of the 6 month follow-up period to those participants for whom we have complete 6 month follow-up information on their demographics, treatment group, and other salient baseline variables. We will account for differential follow-up times due to disenrollment in the Poisson regression model using an offset(46). Because our power calculations are based on excluding all individuals lost-to-follow-up due to disenrollment, these estimates are conservative.

The secondary outcome of emergency department visits will be estimated by Poisson regression in each of the arms, again using generalized estimating equations for the reasons listed above for the primary outcome. The intervention will be compared for non-inferiority to control using a margin of $M=1.5$. This margin of 1.5 for the rate ratio represents a threshold for the relative increase of 50%, beyond which we would consider unacceptable. Sikirica (2014) observed an annual rate of 0.39 per year among adolescents with attention deficit/hyperactivity disorder who were taking antipsychotics(47). Using an estimated rate of emergency department visits of 0.0325 per month on control(47), the non-inferiority margin of 1.5 for the incidence rate ratio would represent a corresponding maximum acceptable rate of 0.0488 per month in the intervention arm. If the rate of emergency department use is greater than expected, say 0.05, then the non-inferiority margin of 1.5 would correspond to a maximum rate of 0.075 in the intervention arm. The estimated treatment effect (emergency department rate on algorithm

divided by the rate on control, estimated by Poisson regression) and 95% two-sided confidence interval (CI) will be compared to the non-inferiority margin (overall: $M = 1.5$) and non-inferiority of the algorithm approach will be declared if the entire coverage of the 95% CI is less than 1.5.

In safety review reports, the ratio between arms of emergency department visit rates will be accompanied by a confidence interval and by the non-inferiority margin, 1.5, for reference. Confidence intervals will be defined by estimating the rate ratio in 5,000 bootstrap samples. Resampling will be done on the cluster (provider) level and stratified by the presence of any event within each cluster. Quantile-based confidence intervals will be identified using the appropriate percentile corresponding to the Pocock alpha-spending function for interim analyses. Excess harm is observed if the entire coverage of the confidence interval for the rate ratio comparing the greater to the lesser rate of emergency department and urgent care visits is greater than 1.5. (While the final non-inferiority analysis for this safety outcome will use the robust sandwich estimator to ensure correct standard errors, the properties of this estimator are based on asymptotic behavior and small sample size performance may be poor.)

We anticipate initial follow-up of 800 patients, randomized to the two arms, with 720 patients remaining enrolled in the study at 6 months of follow-up (i.e., 10% lost to follow-up). Assuming a $P < 0.05$ alpha level, and based on an anticipated 95% of patients in the control arm using antipsychotics at 6 months, this sample will ensure over 95% power to detect a 6% reduction in the percent of participants with any order for antipsychotic medications at 6 months. Furthermore, we expect to have 80% power to detect a 13% reduction in subgroups with exposures occurring with 25% prevalence, and 80% power to detect a 17% reduction in subgroups with exposures occurring with 18% prevalence (e.g., racial/ethnic minorities). A minimal clinically important difference of 10% was pre-specified to allow for evaluation of clinical significance as well as statistical significance. We have over 90% power to detect a 10% reduction in antipsychotic use at 6 months for patients in the intervention arm given a rate of 85%, 90%, or 95% use in the control arm.

As these power calculations are based on the assumed percent of participants on any antipsychotic in the control arm and assumed pattern of intervention effects, we provide examples of detectable intervention effects corresponding to alternative scenarios in the table that follows, including varying rates of subgroup prevalence to evaluate power regarding intervention effectiveness in less prevalent minority groups. In summary, at a range of percentages of participants with any antipsychotic use in the control arm, we will have excellent power to detect a variety of clinically meaningful intervention effects within the expected range.

Using an estimated rate of emergency department visits of 0.0325 per month on control(47) and with a one-sided 0.025 alpha level with equal allocation between groups, we estimate 71% power(48) with 400 patients per arm and 67% power with 360 patients per arm (allowing for loss to follow-up) respectively, to detect equality of emergency department visit rates (i.e., a true rate ratio of 1) in a non-inferiority evaluation with a margin of 1.5. With a greater monthly emergency department rate of 0.05, we would have 88% and 84% power with 400 and 360 patients per arm respectively under otherwise equivalent conditions.

Power under varying percentages of participants in each arm taking antipsychotic medication at 6 months (based on medication orders) and under various subgroup prevalence assumptions.

Subgroup prevalence	n per arm*	Intervention	Control	Power
100%	360	89%	95%	80%
100%	360	85%	95%	>99%
100%	360	80%	90%	97%
100%	360	75%	85%	92%
25%	90	82%	95%	80%
18%	65	78%	95%	80%
10%	36	75%	95%	67%
5%	18	65%	95%	62%

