10 ASSESSMENT OF SAFETY

10.1 Specification of Safety Parameters

It is not feasible to report incidental adverse events (AEs) for this pragmatic trial. Study staff do not have contact with control arm patients. Only intervention arm patients have contact with study staff, resulting in an inability to compare rates of incidental AEs between arms.

We will compare the number and rate of emergency room and urgent care visits, inpatient hospitalizations (psychiatric and non-psychiatric), suicide attempt (fatal and non-fatal), and deaths from all causes to monitor for potential harm to subjects. Comparisons of safety signals between arms will be made and reported to the DSMB 3 times per year. The PI and site investigators will be blinded to the results of these assessments.

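### Does stratifying the DSMB harm bootstrap by whether a provider had any event make the interval far too narrow?

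*Protocol*

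**What the plan says.** Protocol section 8.2.1 describes how the emergency department and urgent care rate ratio is shown in safety reports:

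- Method: "Confidence intervals will be defined by estimating the rate ratio in 5,000 bootstrap samples".
- Resampling unit and strata: "Resampling will be done on the cluster (provider) level and stratified by the presence of any event within each cluster". Study arm is not named as a stratum.
- Level: "Quantile-based confidence intervals will be identified using the appropriate percentile corresponding to the Pocock alpha-spending function for interim analyses".
- Decision rule: "Excess harm is observed if the entire coverage of the confidence interval for the rate ratio comparing the greater to the lesser rate" of these visits lies above 1.5.
- Reason for not using the sandwich estimator at interim looks: "the properties of this estimator are based on asymptotic behavior and small sample size performance may be poor".

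Section 10.1 sets the frequency: "Comparisons of safety signals between arms will be made and reported to the DSMB 3 times per year". The SAP neither repeats nor changes this bootstrap. Its Secondary analysis I covers only the final comparison with the 1.5 margin, by GEE with robust standard errors.

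**The concern.** Bootstrap strata should normally be features fixed by design, such as arm, site or randomization block. Here the stratum is built from the outcome being monitored. Visits are rare, and a provider with few patients who has any event will usually have exactly one. Most of the sampling variation in an arm's event count then lies in how many of its providers have an event at all. If every resample holds that number constant, most of the variance is gone and no Pocock percentile brings it back. The DSMB would see intervals that are too tight, with false harm signals most likely at early, sparse looks. Because the rule compares the greater with the lesser rate, these could point in either direction.

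The size would be serious. With 200 providers of two patients per arm, coverage would be 74% instead of 95%. With 50 providers of two patients and three months of follow-up, false harm flags at one look would be 9.7% instead of 0.7%.

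**Working it through.** **Inputs.** From Protocol section 8.2.1: control rate 0.0325 visits per month, margin 1.5, one-sided alpha 0.025, 400 or 360 patients per arm. Follow-up is 6 months (section 4), so a patient has 6 × 0.0325 = 0.195 expected visits. Assumed, because the documents do not say: 25 to 200 enrolling providers per arm with 1 to 10 patients each, with and without extra variation between providers.

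**1. The plan's own figures.** Power = Φ(ln 1.5 / √(2/(6 × n × rate)) − 1.96).

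- Rate 0.0325, n = 400: 78 expected events per arm; 0.4055/0.1601 − 1.96 = 0.572; power 71.6% (stated 71%).
- Rate 0.0325, n = 360: 67.1% (stated 67%).
- Rate 0.05: 88.1% and 84.6% (stated 88% and 84%).

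The inputs are therefore read as the plan intends.

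**2. What the stated strata fix.** Suppose E1 and E0 providers in the two arms have an event. The sentence as written draws E1 + E0 providers from the pooled event group and the remainder from the pooled no-event group. The number of drawn event providers that belong to the intervention arm is binomial, so it varies from resample to resample. Only the total is fixed.

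**3. Exact case: 200 providers per arm, one patient each, true ratio 1.**

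- Share of providers with an event: p = 1 − e^(−0.195) = 0.1772, so 35.43 per arm.
- Events per event provider: mean 0.195/0.1772 = 1.1007, variance 0.1038, squared coefficient of variation (CV²) 0.0857.
- True sampling variance of the log rate ratio: 2/(200 × 0.195) = 0.0513; SD 0.226.
- Bootstrap variance, event strata only: 2(1 − p + CV²)/35.43 = 2 × 0.9085/35.43 = 0.0513; SD 0.226. Nothing is lost.
- Bootstrap variance, event strata within each arm: 2 × CV²/35.43 = 0.0048; SD 0.070, or 31% of the truth.

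The loss thus comes entirely from crossing the event strata with arm.

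**4. Simulation, true ratio 1, equal panels.** Each cell gives the mean bootstrap SD divided by the true SD, then coverage of the 95% percentile interval (mostly 600 trials × 600 resamples).

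| Providers per arm × patients | Within arm, no event strata | Event strata only (as written) | Event strata within arm |
|---|---|---|---|
| 200 × 1 | 0.98, 94.5% | 0.97, 94.3% | 0.28, 46.8% |
| 100 × 2 | 0.97, 93.3% | 0.97, 93.0% | 0.38, 58.2% |
| 100 × 4 | 1.05, 95.5% | 1.04, 95.2% | 0.59, 76.5% |
| 50 × 8 | 1.00, 95.5% | 0.99, 94.8% | 0.74, 85.8% |

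**5. False flags, same column order.**

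- True ratio exactly 1.5, nominal 2.5%: 2.3%, 3.0%, 19.2% at 100 × 2; 1.8%, 2.5%, 24.7% at 200 × 1.
- True ratio 1, long-tailed panels, 50 × 2, three months, 95% interval: 0.7%, 0.5%, 9.8%.
- The same early case at an assumed first Pocock look (two-sided 0.0126): 0.2%, 0.2%, 7.7%.

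**6. Source of the alarming figures.** With long-tailed panels at 200 × 2, coverage and median log-width are 94.0% and 0.63 without event strata, 93.5% and 0.63 as written, and 76.0% and 0.38 with event strata within arm. The 74% coverage, the 0.38 width and the 9.7% flag rate therefore belong to a procedure that the protocol does not state.

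**The case for a change.** The strongest reply is that resampling within arm is the usual two-sample bootstrap. A programmer could add it unprompted, and the protocol does not rule it out. The likeliest reason for event strata is to avoid resamples in which an arm has no events. Pooled strata do not ensure that: about 0.3% to 0.4% of resamples in a sparse scenario still had an empty arm, against none with arm-by-event strata. The interval also matters, since it defines excess harm and goes to the DSMB three times a year.

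Part of this stands. The text gives no reason for stratifying on events, and it does not say whether arm is a further stratum. If the code did cross the two, the undercoverage would be real. But the motive is inferred, not documented, and the plan has to be judged on the procedure it states. That procedure needs no added step and behaves almost exactly like a bootstrap without event strata. The consequences are also bounded: section 10.2 makes halting a matter for the IRB, NIMH or the DSMB and sets no automatic stop, and the final non-inferiority conclusion uses the sandwich estimator.

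**Conclusion.** The concern does not hold. Followed as written, the bootstrap keeps essentially its full width. In the main simulations its SD is 0.91 to 1.09 times the true value and coverage is 92% to 95%; removing the event strata gives 0.92 to 1.10 and 93% to 96%. Taking all simulation runs together, coverage is 90% to 96% as written and 91% to 96% without event strata. A severe loss appears only if arm is added as a stratum (SD ratio 0.28 to 0.82, coverage 47% to 90% in the main simulations), and neither document calls for that.

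The result rests on reading event status as the only stratum and on the assumed provider numbers and panel sizes. It leaves out very sparse looks of about 8 events per arm, where resamples with no events in an arm make the coverage estimates unreliable. What remains is a missing implementation detail, not an error: as the sentence stands it yields sound intervals, and removing the event strata would change no result materially.
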